Troublesome cough, nasal stuffiness and rhinorrhea (runny nose) are common symptoms associated with viral upper respiratory tract infections (URTIs). These symptoms may persist for many weeks, and contribute to a significant percentage of patient visits to GPs each year (estimated to be about 6% of general practice consultations¹. The diagnosis of post viral cough is highly variable, with poor agreement on the causation being labelled as bronchitis, post nasal drip or sinus problems. Antibiotics are commonly prescribed in this situation, particularly if the patient reports coloured mucus², yet the evidence suggests a limited and problematic role for antibiotics for post viral cough. The National Prescribing Service (NPS) has produced patient education resources promoting the benefit of treatments such as nasal saline, steam inhalation and decongestants over antibiotics for viral URTIs.

Nasal saline irrigation is a popular treatment for sinonasal conditions. Its potential mechanism for alleviating upper respiratory symptoms is by clearing excess mucous, reducing congestion and improving breathing.³ It is reported to increase the frequency of nasal ciliary beating, thereby improving mucociliary clearance.⁴ In addition to relieving sinonasal symptoms, nasal saline irrigation may also remove

infectious material from the sinuses and reduce cough associated with post-nasal drip.⁵

The research literature suggests a clinically significant benefit of nasal saline in the treatment of cough associated with chronic rhinosinusitis and established sinus infections, and for assisting mucociliary clearance.³ However, studies investigating the clinical benefit of nasal saline in acute URTIs are predominantly small and methodologically flawed, although they do suggest some benefit.⁶ No studies on the benefit of saline nasal spray when post viral cough was the presenting symptom were identified, and none that documented the reduction in antibiotic usage by the adoption of this treatment strategy.

This project explores these issues through an open label, randomised clinical trial which aims to compare the effectiveness of the addition of nasal saline spray to usual treatment. The duration of cough as well as the use of other treatments, including antibiotics, will be documented in both groups.

Methods

Research Design – randomised controlled open label trial.

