Randomisation and allocation to study groups – patients will be randomised to either the intervention or control group. Randomising will be done at the Discipline of General Practice using computer generated random sequences in blocks of ten patients. A set of sealed, opaque, sequentially numbered study packs will be delivered to each participating general practice. Once a patient has consented to participate in the study, they will be allocated a study identifier, and will be given a study pack. The study pack will contain the first fortnight's patient diary, and sufficient study medication for a fortnight. Study packs for the control group will contain 3 packs of Vicks Vapor Drops or similar, of comparable size to the nasal saline spray. This will be a 'thank you' to control group participants and will ensure that all study packs look similar such that practice staff and patients remain blinded to group allocation.

Intervention – the intervention is a nasal saline solution which will be used for a minimum of 4 times per day.

Control – patients allocated to the control group will use usual care treatments only.

Primary outcome measure is the return of wellness, indicated by the patients' assessment of the first day of wellbeing.

Secondary outcome measures include:

1. severity and duration of troublesome nasal stuffiness
2. severity and duration of troublesome cough
3. severity and duration of rhinorrhea
4. severity and duration of malaise
5. antibiotic use
6. adverse effects of treatment
7. patient compliance
8. patient satisfaction.

Data collection – The data will be collected through patient diaries. Patients will be completed on a daily basis until general wellbeing is restored or for 6 weeks, whichever occurs first. Answers will be an indicator of the patients' subjective assessment of the severity of the symptoms each day. Restoration of general wellbeing is defined as when the patient answers 'yes' to the question 'Are you well

again?'. The diary has been adapted from one used by general practice researchers in the UK.⁷

A patient enrolment form will be used to gather basic demographic information, the duration of unwellness prior to attending the GP, and the patient's belief about the effectiveness of antibiotics for treating common cold or acute rhinosinusitis.

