Patients' satisfaction with their involvement in the study and, for the nasal saline group, use of the study medication, will be assessed at the time of the final follow-up phone call by asking for patient feedback.

Follow-up – All study patients will be contacted by telephone by the Research Assistant (RA) within 2-3 days of recruitment to ensure understanding and willingness to comply with the study protocol. The RA will contact the patients again 7-9 days after recruitment to determine if symptoms have resolved or whether the patient requires another study pack. A third follow-up call will occur at about day 20, and a third study pack sent out as required. Any patients continuing the treatment / diary at the third call will receive a final follow up telephone call at 6 weeks post enrolment into the study to remind them to send back the symptom diary. The RA will remain blinded to the group to which the patient has been allocated throughout the follow-up period. Another member of staff will make up additional study packs as required.

Analysis – Data will be analysed according to the intention-to-treat principle, comparing the intervention group with the control group. Baseline characteristics and symptoms will be compared using either Student's t-test (for continuous data) or Fisher's Exact Test (for categorical data). We will analyse first day of well-being using Cox regression survival analysis, and will adjust for baseline symptom severity, and duration of illness before visiting the GP. We shall investigate the severity of illness using a symptom score collected on day 3 after enrolment. We will use a multivariate linear regression, adjusting for baseline symptom severity, and duration of illness before visiting the GP. A P-value < 0.05 will be considered statistically significant. There will be no adjustment for multiple comparisons.

Dissemination of results – The outcomes of this study will be disseminated through presentations at relevant conferences, and publication in international peer reviewed journals.

Potential Benefit of Findings

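### The only safety outcome is worded by cause in an open-label, diary-based trial where one arm uses a nasal product, so local events may be reported more often on saline even if saline adds no harm

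*Protocol*

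**What the plan says.** Under Secondary outcome measures, the sixth of eight items is "adverse effects of treatment". It is the only safety outcome, and the protocol neither defines it nor says who decides whether an effect is due to treatment.

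The surrounding text bears on how it would be reported:

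- **Design.** Methods gives a "randomised controlled open label trial".
- **Blinding.** Randomisation and allocation says the packs are made up to "ensure that all study packs look similar such that practice staff and patients remain blinded to group allocation".
- **Saline arm.** Under Intervention, "the intervention is a nasal saline solution which will be used for a minimum of 4 times per day".
- **Control arm.** Under Control, "patients allocated to the control group will use usual care treatments only". "Study packs for the control group will contain 3 packs of Vicks Vapor Drops or similar", as a thank-you. The Synopsis asks all participants to avoid other nasal sprays, decongestants and steam inhalation.
- **Data source.** Under Data collection, the data come from patient diaries, and the answers are subjective.
- **Final call.** The paragraph before Follow-up seeks feedback on use of the study medication from the saline group only.
- **Analysis.** The general intention-to-treat sentence has the data analysed by "comparing the intervention group with the control group".

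**The concern.** Every participant enters with a cold or acute rhinosinusitis, so a sore nose, a nosebleed or a headache can arise from the illness in either arm. A patient using a spray several times a day has an obvious product to blame for such an event. A control patient has no nasal product to blame. If the outcome admits only events that the patient ascribes to treatment, the same background event may be more likely to be reported on saline than in controls.

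The harm comparison would then mix the effect of saline with the effect of knowing one's allocation. An excess on saline could be background illness, or a real excess could be dismissed as attribution. The pilot is meant to refine trial processes and to inform an adequately powered study, so a safety measure with this weakness could carry over into that study. A later analysis plan could not repair it, because it cannot recover events that the diary never asked about.

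**Working it through.** The protocol gives no adverse-event rate and no power for this outcome, so there is no stated figure to reproduce. The check has two parts.

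**1. Does the text allow differential attribution?**

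- The outcome is conditional on cause (Secondary outcome measures).
- Patients know their arm. The design is open label, and the similar-looking packs hold either a nasal spray or drops, so masking cannot outlast opening the pack.
- Reporting is by the patient and subjective (Data collection).
- Only one arm has a nasal product (Intervention, Control, Synopsis).
- No sentence requires events to be recorded alike in both arms whatever their cause.

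The text therefore permits differential attribution. It does not establish that it will occur.

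**2. How large could it be?**

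From the protocol: n = 30 per arm (Sample Size) and P<0.05 (Analysis).

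Assumed:

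- a true event rate r, equal in both arms
- the share of events attributed to treatment, f1 on saline and f0 in controls
- a two-sided Fisher test, which the protocol names only for baseline comparisons

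Expected counts are 30 × r × f1 and 30 × r × f0. The chance of a false result against saline is the sum, over all pairs (a, b) with a > b and Fisher P<0.05, of Bin(a; 30, r·f1) × Bin(b; 30, r·f0).

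With no control events, the threshold follows directly:

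- 5 v 0: P = 2 × C(30,5)/C(60,5) = 2 × 142,506/5,461,512 = 0.052
- 6 v 0: P = 2 × C(30,6)/C(60,6) = 2 × 593,775/50,063,860 = 0.024

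So six or more attributed events on saline against none in controls give P<0.05. In the all v none case the chance is P(X ≥ 6) with X ~ Bin(30, r).

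| Attributed, saline v control | r = 10% | r = 20% | r = 30% |
|---|---|---|---|
| Half v a quarter: expected counts | 1.5 v 0.75 | 3 v 1.5 | 4.5 v 2.25 |
| Half v a quarter: chance of P<0.05 | 0.2% | 1.9% | 5.3% |
| Half v none: expected counts | 1.5 v 0 | 3 v 0 | 4.5 v 0 |
| Half v none: chance of P<0.05 | 0.3% | 7.3% | 28.9% |
| All v none: expected counts | 3 v 0 | 6 v 0 | 9 v 0 |
| All v none: chance of P<0.05 | 7.3% | 57.2% | 92.3% |
| All events counted in both arms: expected counts | 3 v 3 | 6 v 6 | 9 v 9 |
| All events counted in both arms: chance of P<0.05 | 0.5% | 1.1% | 1.3% |

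The last pair of rows is the benchmark. With cause-neutral counting and equal reporting, the chance stays within the nominal 2.5% in one tail.

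**The case against.** The case against has several sound parts.

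- **The stronger reading is not in the text.** A reader might infer that the same cold-related event counts against saline and is not counted in controls. No sentence says so. That would be a prediction about patients' behaviour drawn from one short list item.
- **Controls are treated too.** They have usual care and the drops, and the word treatment in outcome 6 is not confined to saline. Their count is not zero by definition, so all v none is an extreme and not the expected case.
- **The main cold symptoms are covered.** Stuffiness, cough, rhinorrhea and malaise are outcomes 1 to 4, and the Synopsis compares sore throat in both groups. Only the remaining local events are exposed to the problem.
- **The diary is not shown.** Its question may already be neutral as to cause.
- **No test is specified for outcome 6.** The chances of P<0.05 illustrate the bias and are not properties of the stated analysis.
- **Precision and acceptability.** Thirty per arm says little about harm under any definition, and effects that patients ascribe to the spray are relevant to the secondary question on acceptability.

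These points narrow the concern without removing it. If the diary does ask neutrally, outcome 6 should say so. Attribution can be kept as a description without defining the outcome. It might also be objected that the protocol calls patients blinded, but that statement conflicts with the open-label design and cannot survive the opening of the pack.

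**Conclusion.** The point holds in a limited form. Outcome 6 is worded by cause, patients who know their allocation report it, only one arm has a nasal product, and nothing in the protocol makes recording equal across arms. Local events such as nasal soreness, nosebleed or headache may be over-reported on saline relative to controls with no true difference.

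The size cannot be fixed from the protocol. Under the stated assumptions (background rates of 10% to 30%, equal in both arms, and a Fisher test), the chance of P<0.05 against saline is about 0.2% to 5% at half v a quarter attributed, 0.3% to 29% at half v none, and 7% to 92% at all v none. The range runs from negligible to large, and the documents do not say where in it the trial would fall. They do not support the conclusion that control events go uncounted, or that a false signal is likely. The change is worth making before enrolment because it is cheap and the measure may be reused in the full trial.

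**What to change.** - Reword secondary outcome 6 as adverse events.
- Put the same short event item in the same words in both arms' diaries (for example nasal soreness, nosebleed, headache, other), to be answered whatever the patient thinks the cause is.
- Report the proportion of patients with any event by arm, and the comparison with a 95% CI.
- Report patients' attribution of events to the spray separately, as a description that serves the acceptability question.
- Reconcile the statement under Randomisation and allocation that patients remain blinded with the open-label design under Methods.

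The cost is one diary item and a few lines of protocol text. The diary becomes slightly longer and raw event counts rise in both arms. The change reduces open-label reporting bias but does not remove it, since patients using a spray several times a day may still notice and record more nasal events.

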Common Treatments for Common Colds: A Pilot Study

RESEARCH PROTOCOL

[**Squirting Nasal saline solution Or Routine Treatment (SNORT) Study**]

Investigators

[name], [name], [name], [name], [name]

Aims

This project aims to compare the effectiveness of the addition of nasal saline spray to routine care for minimisation of the symptoms of acute URTIs. It also aims to assess the feasibility of conducting a randomised controlled trial for this purpose in general practice and to refine the processes of the trial.

Synopsis

Over the last few years, the National Prescribing Service (NPS) (<http://www.nps.org.au/>) has conducted regular campaigns aimed at educating the public about appropriate treatments for the common cold. They have continually reinforced the message that common colds are caused by viruses, and therefore antibiotics are likely to have no benefit. The NPS have produced resources to educate the public that treatments such as nasal saline, steam inhalation and decongestants that relieve symptoms are more helpful than antibiotics for common colds and viral upper respiratory tract infections.

However, the effectiveness of isotonic nasal saline spray for relief of common cold or acute rhinosinusitis symptoms has not been adequately evaluated – most studies have been too small or of poor methodological quality. Therefore this pilot study aims to determine the feasibility of conducting a general practice based, randomised controlled trial to assess the efficacy of nasal saline spray on the duration of general unwellness and symptoms associated with the common cold or acute rhinosinusitis.

In this study, consenting patients who have visited their GP because of a common cold or acute rhinosinusitis will be randomised to either nasal saline spray plus usual care or usual care alone. All study participants will be requested to not use steam inhalations, or any nasal decongestants or nasal sprays other than the trial medication for the duration of their participation in this study. The duration of general unwellness, cough, runny or blocked nose and sore throat, as well as the use of other treatments including antibiotics will be compared in both groups. Patients will be followed up until their first day of wellbeing or for 6 weeks, whichever occurs first.

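### The symptom diary stops at the first 'well' answer, so durations of stuffiness, cough and rhinorrhea are cut off by the primary outcome

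*Protocol*

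**What the plan says.** The Synopsis states: "Patients will be followed up until their first day of wellbeing or for 6 weeks, whichever occurs first". Methods, Data collection repeats the rule for the diary, which is to be "completed on a daily basis until general wellbeing is restored or for 6 weeks, whichever occurs first". The same paragraph names the source: "The data will be collected through patient diaries". It defines restored wellbeing as a 'yes' to 'Are you well again?', with no condition on individual symptoms.

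The stopping event is also the endpoint: "Primary outcome measure is the return of wellness, indicated by the patients' assessment of the first day of wellbeing". The secondary outcomes include severity and duration of four symptoms, for example "severity and duration of troublesome cough", together with antibiotic use and adverse effects. Under Research question(s), the outcome line of the PICO summary is itself the duration and severity of stuffiness, cough and rhinorrhea.

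Follow-up describes calls at 2-3 days, at 7-9 days and at about day 20, and a 6-week call only for patients still on treatment or diary at the third call. Their stated purposes are understanding and compliance, whether symptoms have resolved or another pack is needed, diary return and, at the final call, satisfaction. None is described as recording when a symptom ended after the 'well' answer.

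**The concern.** A patient can feel well while a cough or runny nose lingers. The Background says that these symptoms can last many weeks and discusses post-viral cough. For such a patient, the end of the symptom is never observed, because the diary has closed.

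Two things follow. First, recorded durations are too short in both arms. Second, anything that moves the 'well' answer earlier in one arm, including expectation in an open-label trial, also shortens that arm's recorded symptom durations. The secondary durations then partly restate the primary result instead of adding evidence about symptoms. Treating the diary's end as censoring does not solve this, because feeling well is related to the course of the symptoms and the censoring is therefore informative. Nor can a later analysis plan recover days that were never recorded.

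**Working it through.** **No figure to reproduce.** The protocol gives 60 participants, 30 per group, with no assumption about symptom duration or time to wellness. All inputs below are assumptions, chosen to show a range.

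**What is recorded.** From the stopping rule, recorded duration = min(symptom duration, day of first 'yes', 42 days).

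**Model 1.** Exponential durations; mean time to 'well' of 8 days in control and 8/HR on saline; mean cough of c days in both arms, so no true effect. Cough and wellness times are linked by a Gaussian copula with correlation rho. The 42-day cap hardly changes the results.

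With rho = 0 the recorded mean is 1/(1/c + HR/8), with HR = 1 in control:

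- c = 12, HR 1.0: 1/(0.0833 + 0.1250) = 4.80 days in both arms; reduction 0%.
- c = 12, HR 1.2: 1/(0.0833 + 0.1500) = 4.29 v 4.80; reduction 11%.
- c = 6, HR 1.2: 1/(0.1667 + 0.1500) = 3.16 v 1/(0.1667 + 0.1250) = 3.43; reduction 8%.
- c = 12, HR 1.5: 1/(0.0833 + 0.1875) = 3.69 v 4.80; reduction 23%.

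The share of coughs cut short with rho = 0 is (HR/8)/(HR/8 + 1/c). For c = 12 this is 0.1250/0.2083 = 60% in control and, at HR 1.5, 0.1875/0.2708 = 69% on saline.

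Simulation for correlated times gives:

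| Wellness HR | Mean cough (days) | rho | Spurious reduction in recorded mean cough |
|---|---|---|---|
| 1.0 | 12 | 0 to 0.7 | 0% |
| 1.2 | 12 | 0 to 0.7 | 11-13% |
| 1.2 | 6 | 0 to 0.7 | 7-8% |
| 1.5 | 12 | 0 to 0.7 | 23-27% |
| 1.5 | 4 | 0.9 | about 5% |

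In the 23-27% row, 60-82% of coughs are cut short across the two arms. In the last row only 10% of control coughs are.

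**Model 2, a check on the form.** Log-normal durations (log-SD 0.6), true median cough 14 days in both arms, correlation 0.6, 30 per arm, Wilcoxon-Mann-Whitney test at 0.05:

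- Median 'well' day 10 v 10: recorded median cough 9.2 v 9.2 days; false-positive rate 4.5%.
- Median 'well' day 10 v 8: recorded 9.2 v 7.7 days; false-positive rate 20%.
- With cough recorded to 42 days regardless of the 'well' answer, the rate is 4.4-5.2%.

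Both models agree on the mechanism: understatement in both arms always, and a difference between arms only when the 'well' day differs.

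**Antibiotic use and adverse effects.** Here only the observation time differs. At an equal assumed hazard of 1% per day, recorded risk is 1 - exp(-0.01 × days): 9.5% over 10 days and 7.7% over 8. This overstates the problem if new antibiotic starts become rare once a patient feels well.

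**The case against.** The strongest case against has several parts.

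- *This is a 60-patient pilot, and the two efficacy analyses it specifies are barely touched.* That stands. Cox regression on the first day of wellbeing is unaffected. The day-3 score is lost only for a patient who is well before day 3. The Analysis paragraph names no model for symptom duration. This lowers the priority, but the pilot also aims to refine trial processes, and an unchanged rule could pass to the larger study.
- *Stuffiness and cough are qualified as troublesome, and a patient who says 'well' is less likely to have a troublesome cough.* Fair. It reduces the share of durations cut short without removing the problem. Rhinorrhea carries no such qualifier. Malaise largely overlaps with not being well.
- *The Background does not say that symptoms outlast the patient's own judgement of being well.* Correct. That they sometimes do is an assumption here.

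A reader might also infer stronger claims that the document does not support.

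- *That any earlier 'well' answer falsely lowers antibiotic use and adverse effects.* Follow-up speaks of treatment and diary continuing together, so the diary probably covers exposure. If saline truly brings wellness sooner, fewer antibiotics would be a real effect.
- *That 23-27% is the expected bias.* It belongs to one unfavourable set of assumptions.
- *That the planned calls could supply a common end-of-window enquiry.* The 6-week call reaches only those still continuing at the third call.

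**Conclusion.** The point holds for the durations of nasal stuffiness, cough and rhinorrhea, and less for malaise. The stopping rule truncates them at the primary event, no other described contact fills the gap, and the loss cannot be repaired in analysis. Understatement in both arms needs only that some symptoms outlast the 'yes'. Bias between arms also needs the 'yes' to come sooner in one arm.

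The size is not derivable from the protocol. Under the assumptions shown, it runs from 0% to 27% of recorded mean cough, depending on the wellness hazard ratio, the length of cough and how closely cough tracks wellness. For antibiotic use and adverse effects the issue is unequal observation time only and is likely small. Because only secondary outcomes of a pilot are affected, this should be fixed, but it does not undermine the trial's main comparison.

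**What to change.** Keep the first 'yes' as the primary endpoint. Continue the daily symptom items after it until each symptom named in the secondary outcomes no longer meets that outcome's own threshold (for stuffiness and cough, no longer troublesome), or to 6 weeks. State the threshold for rhinorrhea and malaise, which have no qualifier. Keep the antibiotic-use item in the diary for the same period.

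State that the extension concerns diary recording only. The Synopsis and the exclusion criteria tie the restriction on other nasal treatments to the duration of participation, so that wording must be reconciled with a diary that runs past the 'well' answer. The follow-up sentence in the Synopsis needs the same edit as Data collection.

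The cost is a few more diary days for patients with lingering symptoms and possibly lower completion late on. The change removes the mechanical cut-off. It does not remove expectation effects on the symptom ratings themselves, which remain subjective and open label.

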Participant recruitment – Participating GPs will opportunistically identify potentially eligible patients as they present for a consultation for treatment of the common cold or acute rhinosinusitis, and initiate discussion to gauge interest and determine eligibility. Following this consultation, the Practice Nurse (or another suitable staff member) will continue discussions with potentially interested patients, answer their questions, and obtain informed consent.

Inclusion criteria

- Patient is aged 2+ years and has had symptoms of cold (runny nose, sore throat, sneezing, cough lethargy etc), or acute rhinosinusitis for at least 5 days and up to but not more than 3 weeks.

Exclusion criteria

Patients who:

- wish to use any treatment involving a volume of liquid going into the nose (e.g. steam inhalations, nasal sprays, nasal decongestant agents nasal douches, neti pot etc). Participants who have previously been using these may be included, provided they agree to discontinue use for the duration of their participation in the study

OR who have:

- known or suspected Chronic Obstructive Pulmonary Disease (COPD)
- suspected pertussis infection
- facial anatomical abnormalities
- cognitive impairment preventing informed consent
- physical impairment preventing compliance with the study protocol

Recruitment of participating GPs – there is a core group of GPs & associated general practices who have been involved in the development of this project – UQ Health Services ([name], [name], [name]), Inala Indigenous Health ([name]) and Inala Primary Care. It is expected that additional GPs will be recruited through the South East Queensland Research Network (a network of GPs who have participated in general practice based, clinical research) and the UQ General Practices of Research Excellence (GPs who have lead clinical research in their own practices).

Sample Size – 60 participants, 30 in each group.

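### Baseline significance tests are uninformative after randomisation and trigger nothing; the substantive gap is that age is in neither stated model, although entry runs from 2 years with no upper limit

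*Protocol*

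**What the plan says.** All places are in the Methods section of the Protocol.

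- **Analysis, baseline:** "Baseline characteristics and symptoms will be compared using either Student's t-test (for continuous data) or Fisher's Exact Test (for categorical data"). One general threshold follows: "A P-value < 0.05 will be considered statistically significant". There is no multiplicity correction. Nothing is said about what happens if a baseline test is significant or not.
- **Analysis, models:** for the primary outcome, the investigators plan a Cox model and "will adjust for baseline symptom severity, and duration of illness before visiting the GP". The linear regression of the day-3 symptom score uses the same two covariates. Both are in the models whatever the baseline tests show.
- **Sample Size:** "60 participants, 30 in each group".
- **Randomisation and allocation:** "computer generated random sequences in blocks of ten patients". Packs go to each practice, but no stratification factor is named.
- **Inclusion criteria:** patients are eligible from age 2, with no upper limit.
- **Data collection:** the enrolment form records basic demographics, prior illness duration and "the patient's belief about the effectiveness of antibiotics for treating common cold or acute rhinosinusitis". Age is not named but is taken here to be one of the demographics.
- **Antibiotic use** is a research question and a secondary outcome. No model is stated for it.

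**The concern.** In a randomised trial any baseline difference between arms is due to chance, so a test of that hypothesis answers a settled question. A small P-value does not show that adjustment is needed. With 30 per arm, a large one does not show that the arms are alike.

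The choice of covariates matters more. Whether a baseline variable belongs in a model should be settled in advance on prognostic grounds. The Protocol does this for severity and prior duration. It does not do it for age, although the population runs from toddlers to the elderly and nothing in the allocation balances age by design. If age predicts time to recovery, leaving it out of the Cox model pulls the hazard ratio toward 1 and loses power, and a chance imbalance in age stays in the estimate from that particular trial. With 60 patients there is little power to spare.

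**Working it through.** The Protocol gives no effect size, SD or power for its 60 patients, so it has no figure of its own to reproduce. Inputs from the Protocol: 30 per arm and a 0.05 threshold. Sidedness is not given; two-sided is assumed.

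**1. Smallest observed gap that reaches P<0.05 (t-test)**

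d = t(0.975, 58 df) × √(2/30) = 2.002 × 0.2582 = 0.517 SD.

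An observed gap of exactly 0.5 SD gives t = 0.5 × √(30/2) = 1.94 and P = 0.058, so it is not flagged. A gap above 0.517 SD always is.

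**2. How often randomisation gives a sizeable gap that passes as non-significant**

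- A gap of 0.3 SD gives t = 0.3 × √15 = 1.16, two-sided P = 0.25. A gap of 0.3 SD or more therefore arises in about 25% of sound randomisations.
- In 5% the gap exceeds 0.517 SD and is flagged.
- Difference: 25% − 5% = about 20%, for one given continuous covariate.

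**3. The same for a yes/no variable (Fisher's test)**

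The Protocol gives no scale for antibiotic belief, so a yes/no item is assumed.

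| Believers, of 30 v 30 | P |
|---|---|
| 12 v 18 | 0.20 |
| 11 v 19 | 0.07 |
| 15 v 23 | 0.060 |
| 15 v 24 | 0.029 |

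From an even split in one arm, nine patients (30 percentage points) must differ before the test flags it.

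**4. Which variables the stated models use**

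| Variable | Recorded | Cox model | Day-3 model |
|---|---|---|---|
| Baseline severity | yes | yes | yes |
| Prior illness duration | yes | yes | yes |
| Age | needed for eligibility | no | no |
| Antibiotic belief | yes | no | no |

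**5. What adding one covariate to the planned Cox model could bring**

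This is a simulation with 400 trials per setting, a true hazard ratio of 2, and two covariates already in the model. All covariate strengths and the hazard ratio are assumptions.

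| Log-HR of added covariate per SD | Power, two covariates | Power, three covariates |
|---|---|---|
| 0 (not prognostic) | about 74% | about 73% |
| 0.3 | about 65% | about 70% |
| 0.5 | about 64% | about 72% |

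The gains are 70 − 65 = 5 and 72 − 64 = 8 points. Each power figure has a simulation error of about √(0.65 × 0.35/400) = 2.4 points, so these are rough sizes. The day-3 regression was not simulated.

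**The case against.** The strongest reply is that the Protocol says only that baseline data will be compared. It draws no conclusion of comparability, selects no covariates and changes no model on the result. That stands, and it rules out three stronger readings that a reader might infer.

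- **That the tests are the only safeguard for age and antibiotic belief.** Randomisation protects against systematic imbalance. A test with no consequence safeguards nothing, so its weakness removes no protection.
- **That the tests miss a half-SD imbalance about half the time.** The t-test would miss a true 0.5 SD population difference 52% of the time, but randomisation excludes such a true difference. The relevant figures concern observed gaps, as in steps 1 and 2.
- **That leaving out antibiotic belief is an error in a stated model.** No model is stated for antibiotic use, and a statistical analysis plan that is not shown may supply one. The Protocol gives the belief item no scale and does not say who answers it for a young child, so adjusting for it could bring in proxy or missing values.

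It can also be said that the two stated covariates are sensible and fixed in advance, that the Protocol nowhere calls age prognostic, and that this is a pilot. All true, and they keep the point modest. But the covariate lists are stated in the Protocol and so can be judged as they stand. Effectiveness is also among the trial's aims, with a significance threshold attached.

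A comparison of an unadjusted model with a one-covariate model would not show what age adds to this plan. The figures in step 5 therefore start from a model that already holds two covariates.

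**Conclusion.** The point holds in a limited form. The baseline tests are uninformative: observed gaps up to 0.517 SD are never flagged, and about one randomisation in five hides a gap of at least 0.3 SD in a given continuous covariate. Removing the tests tidies the reporting and alters no treatment result.

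The part that can alter a result is the absence of age from both stated models in a population with no upper age limit and no named stratification. The estimate across all possible randomisations is not made invalid by this. What is lost is power in the Cox analysis and protection against a chance imbalance in the one trial that is run. The size, roughly 5 to 8 points of power at a hazard ratio of 2, rests on assumed log hazard ratios of 0.3 to 0.5 per SD and on age being recorded at enrolment. If age is not prognostic, nothing meaningful is gained or lost.

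**What to change.** In the Analysis paragraph:

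1. Replace the baseline-testing sentence with a statement that baseline characteristics will be described by arm (mean and SD, or number and percentage) without significance tests, and that no adjustment will depend on observed imbalance.
2. Add age as a pre-specified covariate in the Cox model and in the day-3 regression, beside the two already there, and state the form in which it enters.
3. As a secondary step, where the number of antibiotic users allows, adjust the antibiotic-use comparison for the belief recorded at enrolment. Say first who answers that item for young children and how it is scored.

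Steps 1 and 2 are changes of wording. Age must be known to check eligibility, so no new data are needed, but the enrolment form should name it. The cost of a linear age term is one extra parameter per model. Step 3 carries the risk of proxy or missing belief values and should be kept simple.
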